If successful, this project has tremendous opportunity for RO1 level or Program Level National Funding. As we point out in the text, the specific areas we are targeting were the very ones identified by AHRQ in their 2005 report “Knowledge and Access to Information on Recruitment of Underrepresented Populations to Cancer Clinical Trials.” In addition, we have purposely designed this trial to utilize standardized resources (the NCI pamphlet, the PROMIS measures) so that it is readily exportable to other cancer centers across the country. In our opinion, the use of “home grown” messaging and measurements while methodologically appealing, limits the ability to export the intervention to other settings quickly. Finally the PI and Co-PI of this study are well situated to move the findings from this study to a more National level. [name] serves as Chair of the ASCO Health Disparities Advisory group and is a cadre member of the Alliance cooperative group (formerly CALGB, NCTTG, and ACOSOG) health disparities committee. [name] has served in a leadership role on numerous AHRQ-, NIH- and foundation-funded projects and has

received funding from multiple National bodies including ACS, AHRQ, NCI, and NHLBI. This funding includes the use of the Talking Touchscreen technology which indicates that it has already been well received by National Funders.

IV. Preliminary Studies

A. University of Chicago Clinical Trial Study

General Findings: Clinical Trial Participation at the University of Chicago

Funding from an ACS-IRG ([name]) and an ASCO Young Investigator Award ([name]) allowed us to perform a paired survey of physicians and 375 new patients (57% white and 34% African American) seen in the cancer clinics at the University of Chicago Medical Center from September 2008-May 2010 to determine oncologist and patient attitudes toward enrollment in therapeutic cancer clinical trials. ⁴³Of the 375 patients approached, 338 (90%) agreed to participate and returned their survey forms.

In terms of health literacy (using one question health literacy screener¹⁰⁰ with those “quite” and “extremely confident” filling out medical forms classified as having high health literacy) 63% of the sample had high health literacy and 37% low health literacy. Whites were more likely than AA to have high health literacy (79% vs. 57%; $p<0.0001$)

Knowledge of clinical trials in general, differed significantly by both race and health literacy status.

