2.3 Study Design

V. Study Design and Methodology **Study Type and Sample Size**

This will be a pilot study performed at an urban academic center in south-side Chicago to collect preliminary data in hopes of conducting a larger, randomized intervention. Based on the last two years in our Thoracic oncology clinic at the University of Chicago, we estimate that 600 new patients will be seen over the 2-year period of this study, an amount that will easily provide the number of patients necessary to fulfill the requirement of this pilot study.

For this study, over 2 years, we will contact 150 new lung cancer patients of which 80% (120) will agree to participate in our study. Based on the current clinical trial portfolio in the Thoracic oncology clinic (**see Appendix 5**), which has grown substantially since our last study, it is estimated that trials are now technically available for about 80% of the new patient population (for our pilot of 120 patients that leaves about 100). Of our 100, we estimate, based on our previous work, that a clinical trial will actually be offered to 40% of these patients (40).

Patient Population/Recruitment

All new cancer patients presenting to the University of Chicago outpatient oncology clinics are currently pre-screened for cancer type and set up for appointments by our new patient intake coordinators. New patients with Non-Small Cell Lung cancer and Small Cell carcinoma will be contacted by our study coordinator who will call them 2-3 days prior to their appointment to ascertain their interest in participating in the research study. Those interested will be asked to arrive at their new visit 60-90 minutes prior to the appointment time.

Study Procedure

[figure not shown]
Patients will use the Talking Touchscreen (TT) to complete a pre-intervention survey which will ascertain clinical trial knowledge (detailed in SA#1, surveys in **Appendix 4**) and the following information using the instruments detailed in SA#4: socio-demographics, health literacy, anxiety, depression, and social support. They will then use the TT to view the NCI's educational module on "Taking Part in Cancer Treatment Research Studies". (see **Appendix 3** for a sample screen shot). The NCI

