Hypothesis 2a: By providing the patient important information as to the options they may have in terms of their cancer treatment, directly prior to their talking with their physician and through use of an easy interactive tool, such as the proven TT in low-literacy populations, we will not interrupt or decrease the patient experience but enhance the physician-patient interaction, leading to increased participation in clinical trials.

This pilot study will provide to us the opportunity to understand the feasibility of using technology as a way to educate a cancer population about clinical trials within the healthcare environment of a busy, urban hospital setting. We will use this as an opportunity to understand how to integrate technology into clinic flow so that it is not disruptive but rather increases the efficacy of the physician-patient visit by educating patients as to clinical trials before seeing the physician. We estimate that the survey items will take 20-30 minutes to complete and that patients will spend **15-30 minutes with the TT**. Our experience is that 60 minutes is not an unreasonable burden, given the waiting time and other factors associated with a new visit. We will administer a simple evaluation questionnaire following the completion of the patient encounter with the TT, to measure their experience, including degree of difficulty.

Hypothesis 2b: The use of the TT will not effect clinic flow nor pose an additional burden to patient, physician or staff.

The researcher will also complete a simple questionnaire addressing the effect, if any, of introducing technology into the patient visit.

Data Analysis

We will administer a simple evaluation questionnaire to understand the patient's experience with the TT. We will adapt other questionnaires used in a previous TT study and will calculate descriptive summaries of the responses.

Specific Aim 3: *To evaluate the proportion of patients who sign consent to enroll in a cancer-specific treatment clinical trial when one is offered, compared to historical data.*

At the completion of the physician visit for that day, physicians will fill out a previously validated form asking the following questions:

- Is there a clinical trial here for this cancer and stage, regardless of the patient's other characteristics?
- Did you discuss a clinical trial with this patient?
- Did the patient specifically ask you about a clinical trial before you brought it up?

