- Was the patient offered participation in a treatment-related clinical trial?
- If offered, did the patient sign consent?

Actual enrollment in a clinical trial (signed consent) will be confirmed using linkage to our clinical trial database, e-VELOS, which we used successfully in our previous study.

In our previous trial, 40% of patients offered a clinical trial enrolled in a trial. For our low literacy population, 30% enrolled when offered. We expect to be able to improve on these baseline values both by increasing patient understanding of the trial process and by improving their communication with their physician.

Specific Aim 4: To evaluate the associations between socio-demographics, health literacy, patient-reported outcomes (anxiety, depression, social support) and clinical trial enrollment, using the Behavioral Model for Vulnerable Populations.²⁵

Instruments

Tables 3 and 4 contain the instruments we will use:

TABLE 3: PROMIS INSTRUMENTS (www.nihpromis.org)

Construct	Social Support Measure Tools	Scoring for all PROMIS Psychometrics	Background Information/Psychometrics
PROMIS Companionship Scale	PROMIS V 2.0 short form-4 items. .	Reliability: The degree to which a measure is free of error. It can be estimated by the	PROMIS developed several instruments to measure the quality of social support, which refers to functional aspects of supportive relationships, i.e., interpersonal

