	
Three subscales on the pre- and post-questionnaire will assess attitudes towards clinical trials, knowledge about clinical trials and perceived ability. Change scores will be calculated and evaluated using a paired t-test. A sample size of 120 will have 80% power to detect an effect size as small as 0.258 using a paired t-test with a 0.050 two-sided significance level.
 
Based on our previous study, we estimate that 60% of these patients will have high health literacy (72) and the remaining 40% (48) will have low health literacy. We will evaluate differences in pre- and post-test changes by health literacy group. We will also estimate the correlation between change scores and the continuous measure of health literacy.
 
For Specific Aims 3 and 4: Based on the current clinical trial portfolio in the Thoracic oncology clinic (see Appendix 4), it is estimated that trials are available for 80% of the new patient population (including patient eligibility) (100 patients over 2 years) and of these, 40% will be offered participation (40). Our previous data suggested that when offered, 40% of these patients will sign consent. We hypothesize that our TT intervention will increase both the percentage of patients offered a trial (because of active participation from the patient in inquiring about trials) and in the percentage of patients who sign when offered. These impacts will be most profound in the low literacy group.
 
An effect size of 0.20 (H0: 0.4, HA:0.6) is a reasonable estimate for this pilot to be able to produce a clinically significant improvement in cancer clinical trial enrollment. A sample size of 40 (those offered enrollment) should give us 80% power to detect a 20% difference in trial enrollment from our baseline hypothesized value of 40% at a one-sided alpha level of 0.05.

2.8 Specific Drug Supply Requirements
	
NA

2.9 Adverse Experience Reporting
	
NA

2.10 Itemized Study Budget
	
A preliminary study budget must be provided with the initial proposal submitted to give guidance to the MISP Review Committee as to the expected study costs. A refined itemized budget detailing the costs associated with the study should be provided with the final protocol or included in the study agreement as Exhibit B.

References

1. Comis RL, [name] JD, Aldige CR, et al: Public attitudes toward participation in cancer clinical trials. *J Clin Oncol* 21:830-5, 2003

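### Aim 3 tests thoracic (plus gastric) patients against a fixed 40% signing rate from an all-cancer-clinic survey of 2008-2010, so a clinic, case-mix or period difference cannot be told apart from a Talking Touchscreen (TT) effect, in either direction

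*Combined protocol and SAP*

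**What the plan says.** Aim 3 (section 2.5) evaluates the proportion signing consent "when one is offered, compared to historical data". The baseline is given there: "In our previous trial, 40% of patients offered a clinical trial enrolled in a trial".

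Section 2.7 makes this the null hypothesis, 0.4 against an alternative of 0.6. It says "Our previous data suggested that when offered, 40% of these patients will sign consent", then "A sample size of 40 (those offered enrollment) should give us 80% power" for a 20-point difference "at a one-sided alpha level of 0.05".

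The source of the 40% is the team's earlier survey, described in section 2.2 (Preliminary Studies, A). Its patients were new patients "seen in the cancer clinics at the University of Chicago Medical Center from September 2008-May 2010". Table 1 of that section reports 57% with a trial available, 35% of those offered one, and 41% of those offered signing.

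The present study recruits new lung cancer patients in the thoracic clinic (section 2.3), and section 2.2 adds the gastric cancer clinic. Section 2.3 says of the thoracic trial portfolio: "which has grown substantially since our last study, it is estimated that trials are now technically available for about 80% of the new patient population".

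**The concern.** The benchmark and the study differ in tumour type, calendar period and trials on offer. The plan allows for this where availability is concerned, replacing 57% by 80%, and it moves the offer rate from 35% to 40%. The quantity actually tested, signing when offered, goes from 41% in Table 1 to 40% in the test, with no reason given for expecting the old all-clinic rate to apply here.

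The historical comparison is not matched, standardised or adjusted. The Aim 4 regression controls for stage and line of therapy only among study participants, so it does not touch the Aim 3 comparison.

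Aim 3 is the plan's only comparison of enrollment with and without TT, and the study is meant to inform a larger randomized one. A result above 40% could reflect who attends this clinic and which trials it offers. A result near 40% could hide a real gain.

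**Working it through.** **Inputs.** From section 2.7: n = 40 offered, null 0.40, alternative 0.60, one-sided alpha 0.05. From section 2.2: 338 survey participants, and Table 1 rates of 57% (available), 35% (offered if available), 41% (signed if offered) and 10% (signed overall). From section 2.3: about 600 new thoracic patients over two years, 150 contacted, 80% agreeing, 80% availability, 40% offered. The signing rate in the current clinics without TT is not in the documents, so it is varied as an assumption.

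**1. The plan's own power.** For an exact one-sample binomial test, take the smallest r with P(X ≥ r | 40, 0.40) ≤ 0.05.
- P(X ≥ 21 | 0.40) = 0.074, too large.
- P(X ≥ 22 | 0.40) = 0.039, so the cut-off is 22 of 40.
- Power = P(X ≥ 22 | 40, 0.60) = 0.791.

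The stated 80% reproduces to within a point. The arithmetic is sound; the comparator is the problem.

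**2. The same rule when TT does nothing.** P(X ≥ 22 | 40, p), where p is the assumed no-TT signing rate:

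| Assumed no-TT rate | Chance of declaring success |
|---|---|
| 37% | 1.5% |
| 40% | 3.9% |
| 45% | 13.3% |
| 50% | 31.8% |
| 55% | 56.5% |

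The error also runs the other way. If the no-TT rate were 37% and TT added the planned 20 points, the true rate would be 57% and P(X ≥ 22 | 40, 0.57) = 0.66, against the planned 0.79.

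**3. Precision of the 40%.** The number offered in the survey is not stated. Table 1 allows two approximations.
- Forward: 338 × 0.57 × 0.35 = 67 offered, and 67 × 0.41 = 27 to 28 signed. Exact 95% intervals are 28% to 53% (27/67) and 30% to 54% (28/67).
- Backward: 10% of 338 = 34 signed, and 34 / 0.41 = 83 offered. The exact 95% interval is 30% to 52%.

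So the fixed null has an interval of roughly 28% to 54%. Even with identical populations, computing the cut-off from an estimate of this size as if it were known gives a true one-sided error of about 7% to 8% (true rate 40%, 67 to 83 historical patients).

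**4. What a concurrent comparison could show.** Uncontacted thoracic patients: 600 − 150 = 450. On the plan's rates, signed consents per new patient without TT are 0.8 × 0.4 × 0.4 = 12.8%. With signing raised to 60% they are 0.8 × 0.4 × 0.6 = 19.2%. Counting everyone contacted, with 80% using TT, gives 0.8 × 19.2% + 0.2 × 12.8% = 17.9%.
- Difference: 17.9 − 12.8 = 5.1 points.
- SE = √(0.179 × 0.821/150 + 0.128 × 0.872/450) = 0.035.
- 95% half-width = 1.96 × 0.035 = 6.9 points.
- Power at the 0.05 level: about 31% two-sided, 43% one-sided.

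**The case against.** The best defence is that this is a declared pilot with an openly historical comparison, written as a hypothesis and meant to lead to a randomized study. The benchmark comes from the same institution, also from new patients who agreed to take part, with the same trial-database linkage. Conditioning on being offered a trial removes the direct effect of greater availability, and the physician form records availability, discussion, offer and signing separately.

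Much of this stands. It makes the limitation one of interpretation and no reason to stop the study. It does not make the 40% suitable as a fixed null. The mix of tumours, stages and trials among those offered remains uncontrolled, and section 2.7 still plans a formal powered test.

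A reader might infer more than the documents support:
- **That the clinics are shown to differ in signing rates.** The 33% to 63% spread in Table 1 is by race and health literacy, with p-values of 0.2 and 0.6. The 33% and the 72-76% quoted in the background come from a breast cancer study and a UK trial. None of these compares clinics or periods at this centre.
- **That more trials mean more signing.** In Table 1, African American patients had lower availability than white patients (46% vs 61%) but a higher signing rate (63% vs 37%).
- **That the bias favours TT.** Its direction is unknown; at 37% the test is conservative.

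**Conclusion.** The concern holds as a limit on attribution. Aim 3 can show whether signing when offered exceeds 40%. It cannot show whether TT is the reason, nor rule out that a TT gain was masked.

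The size depends wholly on the unknown no-TT rate. The chance of a false success is 1.5% at 37%, the nominal 3.9% at 40%, and 32% at 50%. These rates are assumptions. The documents establish neither the size nor the direction of a difference, so one cannot conclude that a positive result would probably be spurious. The imprecision of the 40% adds to the problem; that part rests on denominators reconstructed from Table 1.

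The point is worth settling before recruitment is complete, because the concurrent comparison in the fix depends on how patients are chosen for contact.

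**What to change.** 1. **Same-clinic benchmark.** From the team's earlier survey, report signed-if-offered for thoracic and gastric patients, with numerator, denominator and confidence interval, beside the all-cancer 40%. This addresses clinic but not period, and the subset will be small.
2. **Supportive concurrent comparison.** Choose whom to call by a fixed rule, such as every nth new patient on the intake list. Using e-VELOS, compare signed consents per new thoracic patient between everyone contacted (about 150, whether or not they agreed) and those not contacted (about 450). Keep decliners in the contacted group; otherwise volunteers are compared with all comers. Leave it unadjusted unless stage and line of therapy are already recorded for both groups; the plan describes e-VELOS only as confirming consent. The documents give no count of new gastric patients, so the 450 covers thoracic patients only.
3. **Reporting.** Present Aim 3 as an estimate with a confidence interval. Word a positive finding as higher than the historical rate, and not as an effect of TT, unless the concurrent comparison also favours the contacted group.

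**Cost.** Protocol wording, a re-tabulation of existing survey data, a database query and probably an ethics waiver for aggregate counts; no extra patients or visits. The concurrent comparison is imprecise (about ±7 points, power about 30-40% on the assumed rates), and including decliners dilutes the effect. A null result there would be uninformative and should not be read as evidence against TT.

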- High vs. Low HL: 77% vs. 48% ($p<0.0001$)
- White vs. AA: 83% vs. 56% ($p<0.0001$)

Clinical Trial Participation

As shown in **Table 1** below, overall 10% of our patients signed consent for a therapeutic clinical trial with African American patients more likely to sign consent. When a trial is available and offered, 41% of all patients and 63% of our African American patients sign consent. Those with higher health literacy are more likely to sign consent and to sign when offered.

Table 1: Clinical Trial Participation

	All	W	AA	p-value	HHL	LHL	p-value
Signed Consent	10%	10%	18%	0.07	12%	7%	0.2
Clinical Trial Available	57%	61%	46%	0.06	58%	54%	0.69
Offered if Available	35%	36%	31%	0.7	37%	30%	0.47
Signed if Offered	41%	37%	63%	0.2	42%	33%	0.6

W-White; AA-African American; HHH-High Health Literacy; LHL-Low Health Literacy

To better understand the findings regarding African American race and health literacy, we ran a multivariable logistic regression model that controlled for both variables. As displayed in **Table 2**, when controlling for health literacy, AA are 2 times more likely than whites to enroll in a clinical trial. Similarly, those with high health literacy are 2.5 times as likely to enroll as those with low health literacy, controlling for race.

Table 2-Signed Consent: Logistic Regression Models

	OR (bivariate)	95% CI	OR (multivariable)	95% CI
AA:White	1.9	0.9-3.7	2.1	0.8-5.2
HHL:LHL	1.8	0.6-4.9	2.5	0.8-7.8

These data are consistent with our hypothesis that low health literacy is a potential barrier to trial participation. These results also suggest that the impact may be particularly helpful for our African American patients since low health literacy is an intervenable factor which may be dampening what appears to otherwise be enthusiastic support for trial participation in our patient population.

Barriers to Participation

The number one reason that patients did not consent to a trial if offered was that they felt *overwhelmed by the information* (56%). Measured barriers which correlated with not signing consent if offered were lack of social support ($p=0.05$), lack of emotional support ($p=0.01$), high levels of anxiety (OR 0.51; 95% CI 0.13-1.87) and high levels of depression (OR 0.45;95% CI 0.09-2.08). Despite our *a priori* hypothesis that physician trust would play an important role, no measure of physician/institution trust predicted clinical trial enrollment at the University of Chicago.

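### Aim 3 states its historical signed-if-offered baselines as 40% overall and 30% in low literacy, but the source results are 41% and 33%

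*Combined protocol and SAP*

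**What the plan says.** Section 2.5, under Specific Aim 3, reports two results from the investigators' earlier study: "In our previous trial, 40% of patients offered a clinical trial enrolled in a trial", and "For our low literacy population, 30% enrolled when offered". It then makes them the reference for the new study: "We expect to be able to improve on these baseline values". The same section treats enrollment as signed consent.

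Section 2.7 repeats the 40%, attributes it to previous data, and uses it as the null (0.4 against 0.6) for 40 offered patients, with 80% power at a one-sided 0.05.

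The results themselves are in section 2.2, Preliminary Studies. The text says: "When a trial is available and offered, 41% of all patients and 63% of our African American patients sign consent". The matching row of Table 1 reads "Signed if Offered 41% 37% 63% 0.2 42% 33% 0.6", in the column order all, white, African American, p-value, high literacy, low literacy, p-value. The source figures are therefore 41% overall and 33% in low literacy. Table 1 has percentages and p-values only. The only patient totals given for that survey are 375 approached and 338 participating.

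**The concern.** Aim 3 has no concurrent control, so the historical rate is the whole comparator. Both Aim 3 figures lie below the source figures for the same quantity, and section 2.5 does not say they are rounded. If the source is right, the gap is added to any reported gain. The overall figure is also the null of the only powered enrollment test. Low literacy is the group in which section 2.7 expects the largest effect, and it has the larger mismatch.

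**Working it through.** **Inputs**
- Aim 3 baselines (section 2.5): 40% overall, 30% low literacy.
- Source (section 2.2, text and Table 1): 41% overall, 33% low literacy, 42% high literacy.
- Literacy split (section 2.2): "63% of the sample had high health literacy and 37% low health literacy".
- Trial available (Table 1): 54% low literacy, 58% high literacy. Offered if available: 30% and 37%.
- Test (section 2.7): n = 40, null 0.40, alternative 0.60, one-sided 0.05, power 80%. No test is named.

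**1. Size of the mismatch**
- Overall: 41 − 40 = 1 point (0.5 to 1.5, since 41% may be 40.5% to 41.5%). Among 40 offered patients: 0.01 × 40 = 0.4 of a patient.
- Low literacy: 33 − 30 = 3 points (2.5 to 3.5). Section 2.7 expects 48 low-literacy patients. Assuming the plan's 80% availability and 40% offer rates apply to them, 48 × 0.8 × 0.4 = 15.4 are offered, and 0.03 × 15.4 = 0.46 of a patient.

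**2. Is rounding a plausible cause?**
Yes. 41 to 40 and 33 to 30 are both nearest-ten rounding. The plan rounds the same way elsewhere: the 63/37 literacy split becomes 60/40 in section 2.7, and the 35% offered-if-available rate in Table 1 becomes 40% in section 2.3.

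**3. Does Table 1 support its own 41%?**
The overall rate should be the average of the two literacy groups, weighted by their shares of the offered patients. Assuming the 63/37 split applies to the patients in the table:
- Low literacy offered: 0.37 × 0.54 × 0.30 = 0.0599
- High literacy offered: 0.63 × 0.58 × 0.37 = 0.1352
- Low-literacy share of those offered: 0.0599 / (0.0599 + 0.1352) = 0.307
- Implied overall rate: 0.307 × 33% + 0.693 × 42% = 39.2%

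Letting each input vary within its rounding gives 38.6% to 39.9%, so rounding alone does not reach 41%. Missing literacy answers could explain the difference. The overall column does not chain either: 0.57 × 0.35 × 0.41 = 8.2%, against the 10% reported as having signed consent. The true denominators cannot be recovered from the document.

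**4. Effect on the powered test**
One-sample normal approximation:

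power = Φ{ [√n (p1 − p0) − 1.645 √(p0(1 − p0))] / √(p1(1 − p1)) }

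- The plan's own case, p0 = 0.40, p1 = 0.60: (1.265 − 0.806) / 0.490 = 0.937, power 82.6%. This is consistent with the stated 80%.
- p0 = 0.41, p1 = 0.60: (1.202 − 0.809) / 0.490 = 0.802, power 78.9%. Over the rounding range of 41% it is 80.8% (null 0.405) to 76.9% (null 0.415).
- p0 = 0.41, p1 = 0.61 (20-point difference kept): (1.265 − 0.809) / 0.488 = 0.935, power 82.5%.

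The 30% low-literacy figure enters no stated test, so there is no power to recompute for it.

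**The case against.** The strongest reply is that this is ordinary rounding in a pilot and changes nothing of substance. Much of that stands. Rounding is the likeliest cause, the gaps amount to less than half a patient in each case, and the historical rates are themselves imprecise. Chaining Table 1's percentages over all 338 participants (an assumption) suggests about 67 offered patients overall and 20 with low literacy. Exact 95% intervals for nearby counts that fit the table are 29% to 54% (28 of 68) and 15% to 57% (7 of 21). What does not stand is that rounding makes the figures right. The rounded values elsewhere are projections for the new study, whereas section 2.5 reports past results and uses them as the comparator.

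Three stronger readings are tempting, and the documents do not support them.
- **A serious loss of power or of type I error control.** By exact binomial, a rule of 22 or more of 40 has a type I error of 0.039 at a null of 0.40 and 0.052 at 0.41. The cut-off then moves to 23, and power at 0.60 falls from 79% to 69%. But the plan names no test, and the fall is mostly a one-patient step. At a null of 0.405, which also prints as 41%, the rule of 22 stays valid (0.045). At a null of 0.40, going from 40 to 41 patients lowers power to 75% on its own.
- **A figure taken from the wrong row.** The 30% equals the low-literacy cell of the neighboring row, "Offered if Available 35% 36% 31% 0.7 37% 30% 0.47". Rounding explains it equally well, and nothing in the text decides between the two.
- **Baselines set low to favor the intervention.** The same rounding goes upward elsewhere (35% and 37% both become 40%), so no such purpose can be inferred.

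**Conclusion.** The mismatch is real and minor. The firmer part is low literacy: 30% against a source of 33%, so a gain measured against 30% would be overstated by about 3 points if Table 1 is right. That comparison is descriptive only. Overall, 40% against 41% would overstate a gain by about 1 point, but a reader should not take that direction as settled, because Table 1's literacy columns point to about 39%.

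The effect on the powered test is small and depends on which part of the design is held fixed. Power is 78.9%, about one point under the stated 80%, if the alternative stays at 0.60. There is practically no loss (82.5% against 82.6%) if the 20-point difference is kept.

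The conclusion assumes that the earlier study cited in Aim 3 is the survey reported in section 2.2. It is the only enrollment study at this center whose results the protocol gives.

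**What to change.** Before any outcome analysis, take the numbers offered and signed, overall and for low literacy, from the earlier survey and reconcile sections 2.5 and 2.7 with Table 1. Use the resulting unrounded rates (41% and 33% if the counts confirm them) as the Aim 3 comparators and the overall rate as the null. Then restate the power against that null, saying whether the alternative of 0.60 or the 20-point difference is retained.

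The cost is a few lines of wording and counts from the investigators' own survey. The downside is a slightly harder target and possibly a slightly lower stated power.
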